	
Specifically for the amendment of the UK protocol v6.1: Inclusion/Exclusion Criteria.
	
Inclusion criterion 5 broadened to BCVA of 24 letters (6/95 and 20/320 Snellen acuity equivalent) for Cohorts 4 to 7, to allow inclusion of subjects with worse-seeing vision who may benefit from GT005 treatment. This inclusion criterion was previously broadened in the US protocol v7.1, but not the UK protocol v6.1.
 
Exclusion criterion 14 added. This criterion applies to the US-specific cohorts, so was not included in the UK protocol v6.1.

	
Options to perform the visual acuity check pre-surgery.
	
Provided clarification on the possibility to use ETDRS (not only Snellen) for pre-surgery visual acuity check.

	
Specifically for the amendment of the UK protocol v6.1: OCT-A imaging added, if required, to identify potential CNV conversion during the study. OCT-A methodology included.
	
The US- and UK-specific protocols have been combined into a single global protocol. This change was previously made in the US protocol v7.1, but not in the UK protocol v6.1.

Protocol Version	Change	Justification
	
Specifically for the amendment of the UK protocol v6.1: Removal of reference to PRL identification prior to surgery (requirements surrounding PRL identification are described in the surgical manual).
 
Removal of reference to a “central” surgical site.
 
Removal of text describing procedures for destruction of GT005
 
[REDACTED]
 
[REDACTED]
 
[REDACTED]
 
[REDACTED]
 
[REDACTED]
 
[REDACTED]
 
[REDACTED]
 
[REDACTED]
 
[REDACTED]
	
The US- and UK-specific protocols have been combined into a single global protocol. This change was previously made in the US protocol v7.1, but not in the UK protocol v6.1.
 
Clarification of terminology that subjects will undergo subretinal surgery at the study site.
 
This information will be included within the pharmacy manual

	Risk/benefit analysis update to include that GT005 is in early clinical development.	Clarified that the potential risks of GT005 have also been evaluated in preliminary clinical data (in humans).
	Update to reason for screen failure.	Clarified that eligible subjects who do not receive treatment, can be replaced and classed as screen failures.
	Update of the list of options for action taken regarding study drug in the adverse event reporting section.	To more accurately document this information.

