
Abbreviations: BCVA=best corrected visual acuity; CNV=choroidal neovascularisation; ETDRS=early treatment diabetic retinopathy study chart; FA=fluorescein angiography; LLVA=low luminance visual acuity; MAIA=macular integrity assessment; MNRead=Minnesota low vision reading; OCT=optical coherence tomography; OCT-A=optical coherence tomography angiography; Tel=telephone; [REDACTED].
 
1. Dependent upon location and Sponsor approvals, a Surgical Site may also act as a Local Site2. Screening assessments may be conducted over several days. The screening period may be extended up to a maximum of 12 weeks, if agreed by the Sponsor Medical Monitor. If the screening period is extended past the original 8-week screening period (8–12 weeks), standard ophthalmic exam, haematology/biochemistry, and visual acuity (BCVA/LLVA) assessments should be repeated. In the event the GT005 administration is deferred during the surgical procedure (e.g., due to an AE occurring during surgery) the screening period may be extended up to 16 weeks if agreed by the Sponsor Medical Monitor. Additionally, if the screening period is extended past 12 weeks (12–16 weeks), in case of GT005 deferral, standard ophthalmic exam, haematology/biochemistry, visual acuity (BCVA/LLVA), and FAFs will be repeated.3. Pre-surgery assessments should be performed within 7 days prior to surgery.4. Visit 3 will take place at the surgical site, however this may be held at the local site if more practical.5. A pre-surgery ocular safety check will be performed to verify no new adverse events that could halt surgery. [REDACTED]7. Other imaging modalities may be performed to assess for CNV if OCT-A is not available. In the event that the OCT/OCT-A images are inconclusive to rule out the presence of CNV the subject will be required to undergo an additional assessment via FA. At the Investigator's discretion, FA may also be performed initially prior to the OCT/OCT-A results being available, but this is not mandatory.8. OCT-A and/or fluorescein angiography may be performed during the study period if clinically indicated, for example, if a subject converts to wet AMD.9. Microperimetry should be performed during scheduled visits at sites with a MAIA microperimeter: Microperimetry will be performed at either screening or prior to surgery (within the screening visit window) and may be performed over >1 day if needed. If in the view of the Investigator, the subject is not capable of performing the test, this will not be considered an exclusion to study participation. Microperimetry assessment instructions will be provided in the imaging manual.10. If omitted at screening, assessments should be performed during the pre-surgery visit. [REDACTED]12. LLVA is not performed at Visits 3, 4 and 4.1.13. A visual acuity check using ETDRS or Snellen chart (near card is permissible) must be performed on the study eye if >4 weeks have lapsed since the last BCVA with ETDRS assessment. If Snellen result is >3 lines (BCVA equivalent to 15 letters) worse than the previous BCVA ETDRS score, then a BCVA with ETDRS assessment must be repeated. If the BCVA ETDRS score in the study eye is either >15 letters worse than the previous BCVA ETDRS score or <24 letters score (Cohorts 4 to 7), the surgery must be postponed pending discussion and approval by the Sponsor Medical Monitor. [REDACTED]15. Enrolled subjects will be asked if they are willing to consent to have historical FAF and/or OCT images that were obtained within 1 year prior to enrolment, if available, provided to the sponsor.	

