1.9. Population

Subjects with bilateral GA due to AMD in the absence of neovascularisation will be enrolled into the study.

As this is a FIH study, subjects with GA due to AMD and already some vision loss in the study eye have been chosen for Part 1 (Cohorts 1 to 3; dose-escalation). On completion of the dose escalation and review of the safety data by the Data Safety Monitoring Board (DSMB), subjects with better preserved vision, who potentially would be more likely to benefit from treatment, will be entered into Parts 2 (Cohort 4), 3 (Cohorts 5 to 6), and 4 (Cohort 7) of the study.

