The study will, for the individual subjects, consist of up to 13 visits over a 5-year period. All subjects will be assessed for the occurrence of AEs at each visit and will undergo functional visual and retinal imaging/anatomical assessments and biological sampling as per the schedule of assessments.

Following consent, subjects will undergo a number of ophthalmic and clinical assessments to determine eligibility for inclusion in the study. Once eligibility is confirmed by the Sponsor, the subject will be enrolled. The subject will be scheduled for surgery [REDACTED]
[REDACTED]
[REDACTED]

Data from subjects screened in another Gyroscope sponsored study at the same Investigative site as FOCUS may be used to fulfil the screening and eligibility requirements for this study. This is only permissible if the screening data are collected within the screening period specified in the clinical protocol. Following consent, subjects will undergo ophthalmic and clinical assessments to determine eligibility for inclusion in the study. Should subjects fail to meet the eligibility for FOCUS, they will be classed as screen failures for this study and may be considered for entry into another Gyroscope sponsored study.

At the screening visit, baseline assessments will be carried out including ophthalmic examination, measurements of the size of GA, retinal examination, microperimetry and visual acuity (BCVA and LLVA). OCT angiography (OCT-A; or other imaging modality if OCT-A is not available) and fluorescein angiography (FA) may be performed at screening to assess presence of occult CNV. In the event, that the OCT/OCT-A images are inconclusive to rule out the presence of CNV, the subject will be required to undergo an additional assessment via FA. At the Investigator's discretion, FA may also be performed prior to the OCT/OCT-A results being available, but this is not mandatory. Blood samples will be taken for safety assessments, genotyping (if required), immunogenicity assessment as well as standard biochemistry and haematology.

Subretinal surgery and administration of GT005 will take place at a surgical site. Additional tests/procedures not specified within the study protocol but required as per the standard practice of the surgical site may be required to be performed either at the local site or the surgical site in preparation for surgery (e.g., electrocardiogram, Methicillin-resistant Staphylococcus aureus test, Snellen BCVA).

[REDACTED]

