4.2. Inclusion Criteria

For inclusion in the study, subjects must fulfil all of the following criteria:

1. Able and willing to give consent to study participation
2. Have a clinical diagnosis of GA secondary to AMD in the study eye, as determined by the Investigator, and a diagnosis of AMD in the contralateral eye (except if the subject is monocular)
3. Cohorts 1 to 6: GA lesion(s) total size in the study eye must be $\geq 1.25\text{mm}^2$ and $\leq 17.5\text{mm}^2$
Cohort 7: GA lesion(s) total size in the study eye must be $\geq 1.25\text{mm}^2$
4. GA lesion(s) in the study eye must reside completely within the FAF fundus image
5. Cohorts 1 to 3: BCVA of ≤ 50 letters (6/36 Snellen acuity equivalent or worse) using ETDRS charts in the study eye
Cohorts 4 to 7: BCVA of ≥ 24 letters (6/95 and 20/320 Snellen acuity equivalent or better) using ETDRS charts in the study eye
6. Aged ≥ 55 years
7. Able to attend all study visits and complete the study procedures
8. Women of child-bearing potential need to have a negative urine pregnancy test within two weeks prior to receiving the drug. A pregnancy test is not required for postmenopausal women (defined as being at least 12 consecutive months without menses) or those surgically sterilised (those having a bilateral tubal ligation/bilateral salpingectomy, bilateral tubal occlusive procedure, hysterectomy, or bilateral oophorectomy)

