If the screening period is extended past the original 8-week screening period (8–12 weeks), standard ophthalmic exam, haematology/biochemistry, and visual acuity (BCVA/LLVA) assessments should be repeated. In the event, that GT005 administration is deferred during the surgical procedure (e.g., due to an AE occurring during surgery) the screening period may be extended up to 16 weeks if agreed by the Sponsor Medical Monitor. Additionally, if the screening period is extended past 12 weeks (12–16 weeks), in case of GT005 deferral, standard ophthalmic exam, haematology/biochemistry, visual acuity (BCVA/LLVA), and FAFs will be repeated.

Visit 2 will occur at a surgical site. Pre-surgery assessments will include any local requirements of the surgical site. Pre-surgery assessments should be performed within 7 days prior to surgery. The following assessment are also required pre-surgery:

Timing	Procedure
Prior to Entering the Operating Room (within 7 days prior to surgery)	
• Review of Medical/Surgical History including bleeding history• Vital signs• AE/SAE monitoring• Pre-surgery ocular safety check to verify there are no new ocular AEs that would halt surgery• Microperimetry, if this was omitted at screening, should be performed if feasible• Concomitant medication review including use of anti-thrombotic drugs■ [REDACTED]■ [REDACTED]• Urine pregnancy test (for women of childbearing potential) if the one performed at screening is more than 14 days old• Blood draw for:■ [REDACTED]• Visual acuity check:
○ A visual acuity check using ETDRS or Snellen chart (near card is permissible) must be performed on the study eye if >4 weeks have lapsed since the last BCVA with ETDRS assessment. If Snellen result is >3 lines (BCVA equivalent to 15 letters) worse than the previous BCVA ETDRS score, then a BCVA with ETDRS assessment must be repeated. If the BCVA ETDRS score in the study eye is either >15 letters worse than the previous BCVA ETDRS score or <24 letters score (Cohorts 4 to 7), the surgery must be postponed

7.2. Visit 2 Day 2 (Post-Operative discharge); at a Surgical Site:

Subjects will be maintained in the clinic for up to 24 hours following the subretinal injection to assess any acute issues resulting from the surgery. The following post dosing assessments will be performed:

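### The Snellen check before surgery does not re-apply the 24-letter limit for Cohort 4 to 7 eyes last scored at about 24 to 38 letters

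*Protocol*

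**What the plan says.** Section 7.1 (pre-surgery assessments for Visit 2) and Table 2 footnote 13 carry the same rule, in three steps.

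1. **Check.** The permitted charts and the timing are set out thus: "visual acuity check using ETDRS or Snellen chart (near card is permissible) must be performed on the study eye if >4 weeks have lapsed". The interval is counted from the previous ETDRS test.
2. **Repeat.** "If Snellen result is >3 lines (BCVA equivalent to 15 letters) worse than the previous BCVA ETDRS score", an ETDRS test must follow.
3. **Postponement, judged on the ETDRS score.** This applies to a loss of more than 15 letters, "or <24 letters score (Cohorts 4 to 7), the surgery must be postponed pending discussion and approval by the Sponsor Medical Monitor" (footnote 13).

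The 24-letter figure is the entry limit for these cohorts. Inclusion criterion 5 (Section 4.2) asks for "BCVA of ≥ 24 letters (6/95 and 20/320 Snellen acuity equivalent or better) using ETDRS charts in the study eye". Cohorts 1 to 3 have only an upper limit: "BCVA of ≤ 50 letters (6/36 Snellen acuity equivalent or worse) using ETDRS charts in the study eye".

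**The concern.** Step 3 has two conditions, one relative and one absolute. Step 2 mirrors only the relative one. If a site uses Snellen and the reading is below the 24-letter equivalent, nothing requires an ETDRS test unless the loss also exceeds three lines. Without an ETDRS score, the absolute condition in step 3 has nothing to act on.

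Snellen is a plausible route. Section 3.1 mentions local tests "in preparation for surgery (e.g., electrocardiogram, Methicillin-resistant Staphylococcus aureus test, Snellen BCVA", and the V8.0 amendment entry reads "Provided clarification on the possibility to use ETDRS (not only Snellen) for pre-surgery visual acuity check". Neither shows how often Snellen is used for this check. The Section 3.1 sentence concerns tests outside the protocol, and the log entry is context only.

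At stake is whether a review that the sponsor made mandatory takes place before an injection that, as Section 4.4 notes, cannot be removed. At present that can depend on which chart the site picks.

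**Working it through.** **Inputs.** Entry limit of 24 letters (Section 4.2). Snellen trigger of more than 3 lines, equated with 15 letters, and ETDRS postponement at a loss above 15 letters or a score below 24 (both Section 7.1 and Table 2 footnote 13). The protocol's own equivalence gives 15 / 3 = 5 letters per line.

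**Notation.** b is the last ETDRS score (b ≥ 24), and x is the letter equivalent of the Snellen reading.

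- An ETDRS score of x would postpone surgery if b − x > 15 or x < 24.
- The Snellen trigger fires only if b − x > 15.
- The missed cases have x ≤ 23 and b − x ≤ 15, that is, b − 15 ≤ x ≤ 23.
- Such an x exists only if b − 15 ≤ 23, so b ≤ 23 + 15 = 38.

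The affected range is 24 to 38, or 15 whole-letter scores.

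| Last score b | Snellen equivalents below 24 with no repeat required |
|---|---|
| 24 | 9 to 23 |
| 30 | 15 to 23 |
| 38 | 23 only (loss of exactly 15) |
| 39 | none (39 − 23 = 16, trigger fires) |

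**Worked case.** Take b = 30 and x = 18. The loss is 12, so no repeat is required. An ETDRS score of 18 would have required postponement.

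**Alternative reading.** If the trigger means at least four whole lines (4 × 5 = 20 letters), the missed cases have b − x ≤ 19. Then b ≤ 23 + 19 = 42, and the range is 24 to 42.

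**Where the 24-letter condition matters.** From b = 39 upward, any fall below 24 is already a loss of at least 16 letters, so the relative condition covers it. The absolute condition adds something only for b from 24 to 38, which is the range where the Snellen trigger stays silent.

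**After the fix.** A missed case would need x < 24 while the new trigger (b − x > 15 or x < 24) does not fire. No such case exists.

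**Timing and numbers.** The check is mandatory only after more than 4 weeks, and BCVA should be repeated if screening runs past 8 weeks, so the gap lies mainly between 4 and 8 weeks. The rule covers Cohorts 4 to 7: 20 + 5 + 5 + 20 = 50 of about 65 subjects.

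**Other safeguards.** Sponsor confirmation of eligibility uses screening BCVA (Section 7.1). Table 1 marks review of the entry criteria at screening only. The pre-surgery ocular safety check looks for new ocular adverse events and states no acuity floor. Exclusion 13 rests on investigator opinion. Any of these might catch such an eye, as might a voluntary ETDRS repeat, but none requires the review.

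**The case against.** The best defence is that the rule is a deliberate two-step design. Snellen, or a near card, serves as a coarse screen for marked change, and absolute limits are judged only on ETDRS. An eye missed this way has lost no more than the change tolerated on Snellen. Nothing in the documents contradicts this reading, but nothing states it either. It would leave the sponsor's 24-letter rule idle on a permitted route, at the scores where that rule has work to do.

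Several further points stand and limit the weight of the finding:

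- The limit is not shown to be a safety floor. Cohorts 1 to 3 had no lower limit, and Section 1.9 explains the later entry criterion by reference to "subjects with better preserved vision, who potentially would be more likely to benefit from treatment".
- The path is narrow: a Cohort 4 to 7 eye in the affected range, more than 4 weeks since ETDRS, Snellen chosen, and no voluntary repeat.
- No analysis set or primary endpoint changes. SAP Section 2.2 excludes nobody from the SAF or FAS for protocol deviations.
- Dosing may be over. The SAP document history has an entry dated 24-NOV-2023 placed before the final database lock, and SAP Section 3.1 plans a report on all seven cohorts over 96 weeks. This is inference, since the documents do not say that enrolment has closed.
- Some pre-surgery items are redacted and the Surgical Manual is not available, so the absence of a Snellen floor is established only for the visible text.

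**Conclusion.** The concern holds. The Snellen trigger matches one of the two postponement conditions. For last scores of 24 to 38 letters (24 to 42 on the four-line reading), a Snellen result below the 24-letter equivalent can pass with no ETDRS repeat and no Medical Monitor review required.

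This is an inconsistency in re-applying an entry limit. What is lost is a mandatory postponement pending review, not a bar to surgery. The documents do not say how many subjects enter in this range, how many are checked on Snellen, or how many remain to be dosed.

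The ranges assume 5 letters per line, as the protocol's equivalence implies, and are approximate because Snellen is read in lines. The point deserves correction because the rule fails on a route that the protocol permits and the remedy is cheap.

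**What to change.** In Section 7.1 and in Table 2 footnote 13, extend the trigger. After "If Snellen result is >3 lines (BCVA equivalent to 15 letters) worse than the previous BCVA ETDRS score", insert: *or (Cohorts 4 to 7) worse than 6/95 (20/320)*. The requirement to repeat ETDRS then follows as now, and the postponement sentence stays unchanged. The 6/95 (20/320) equivalent is already in inclusion criterion 5.

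The cost is some extra ETDRS tests, including false alarms in eyes that still score 24 or more, and a few postponements that the rule already intends. The documents do not say whether every permitted Snellen chart or near card resolves 6/95. Where one does not, the site can use ETDRS, which the check already allows.

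If dosing is complete, review the pre-surgery Snellen records of dosed Cohort 4 to 7 eyes last scored at 24 to 38 letters (up to 42 on the wider reading), and correct the clause before the text is reused.

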7.17. Unscheduled Visits

7.17.1. Prior to Week 48 Visit

If clinically indicated, subjects may need to return to the site for an unscheduled visit. The Investigator will perform assessments considered to be appropriate for the participant, considering the reason behind the need to arrange an unscheduled visit. These results should be recorded in the subject's medical notes and eCRF.

7.17.2. Post Week 48 to Week 240 Visit

If clinically indicated, subjects may need to return to the site for an unscheduled visit. The following assessments, along with any other assessments that are needed, may be completed at the discretion of the Investigator:

- Recording of AEs and concomitant medication
- Standard ophthalmic examination
- CFP
- FAF
- OCT macula
- OCT-A if clinically indicated (if a subject converts to wet AMD)
- FA if clinically indicated (if a subject converts to wet AMD). FA is only required if OCT/OCT-A images are inconclusive to rule out the presence of CNV. However, FA may also be performed prior to the OCT/OCT-A results being available, but this is not mandatory
- Microperimetry. **Note: microperimetry is only applicable at sites with a MAIA microperimeter**
- Visual Acuity (BCVA and LLVA) using ETDRS

- [REDACTED]
- [REDACTED]

7.18. Early Termination Visit

Subjects have the right to withdraw from the study at any time and for any reason. If a subject refuses to be seen for further visits, the assessments listed in the early

termination visit should be performed at the time they have indicated that they will not attend for further visits.

Where a subject is withdrawn from the study at their own request or based on a decision of the Investigator, follow-up may be maintained, which may include telephone calls or follow-up visits arranged by the investigator, subject to the consent of the participant.

7.18.1. Prior to Week 48 Visit:

In the event that a subject discontinues the study prior to Week 48 visit, the site should use every reasonable effort to ensure that an Early Termination Visit is conducted. The following assessments should be performed:

Recording of: concomitant medication, vital signs, AEs.

The following procedures will be carried out:

- Blood draw for:
 - Biochemistry and haematology
 - [REDACTED]
 - [REDACTED]
 - [REDACTED]
- Standard ophthalmic examination
- CFP
- FAF
- OCT macula
- [REDACTED]
- OCT-A if clinically indicated (if a subject converts to wet AMD)
- FA if clinically indicated (if a subject converts to wet AMD). FA is only required if OCT/OCT-A images are inconclusive to rule out the presence of CNV. However, FA may also be performed prior to the OCT/OCT-A results being available, but this is not mandatory
- Microperimetry. **Note: microperimetry is only applicable at sites with a MAIA microperimeter**
- Visual acuity (BCVA and LLVA) using ETDRS
- [REDACTED]
[REDACTED]
[REDACTED]
- [REDACTED]

7.18.2. Post Week 48 to Week 240 Visit

In the event that a subject discontinues the study after Week 48 and before Week 240 visit, the site should use every reasonable effort to ensure that an Early Termination Visit is conducted. The following assessments should be performed:

Recording of: concomitant medication, vital signs, AEs.

The following procedures will be carried out:

- Blood draw for:
 - Biochemistry and haematology
 - [REDACTED]
 - [REDACTED]
 - [REDACTED]
- Standard ophthalmic examination
- CFP
- FAF
- OCT macula
- [REDACTED]
- OCT-A if clinically indicated (if a subject converts to wet AMD)
- FA if clinically indicated (if a subject converts to wet AMD). FA is only required if OCT/OCT-A images are inconclusive to rule out the presence of CNV. However, FA may also be performed prior to the OCT/OCT-A results being available, but this is not mandatory
- Microperimetry. **Note: microperimetry is only applicable at sites with a MAIA microperimeter**
- Visual acuity (BCVA and LLVA) using ETDRS
- [REDACTED]

